7.4 Reporting Procedures

The site staff must immediately report to the coordinating center PI any serious adverse event, whether or not considered study related, including those listed in the protocol and must include an assessment of whether there is a reasonable possibility that the study caused the event within 48 hours of PI awareness of the event.

They must also report any unanticipated problems within the same timeframe. The Site staff must also report any protocol deviations or violations to the coordinating center PI within 7 days of awareness. Participating centers must also submit all reports to their local IRB in accordance with their institutional policies.

SAEs that are unanticipated, serious (Grade 3), and possibly related to the study intervention will be reported to the Independent Monitors, IRB, and NICHD in accordance with requirements.

Unexpected fatal or life-threatening AEs related to the intervention will be reported to the NICHD Program Officer and Independent Monitoring Committee within 2 days and to the IRB within 1 day. Other serious and unexpected AEs related to the intervention will be reported to the NICHD Program Official within 7 days.

Other anticipated or unrelated SAEs will be handled in a less urgent manner but will be reported to the Independent Monitor(s), IRB, NICHD, and other oversight organizations in accordance with their requirements. In the annual AE summary, the Independent Monitor(s) Report will state that they have reviewed all AE reports.

7.5 Follow-up for Adverse Events

In instances where an adverse event does occur, we will follow-up with participants until the event is resolved or until the IRB deems it unnecessary to continue to follow the participant.

7.6 Safety Monitoring

We have developed a Data Safety and Monitoring Plan which oversees the progress of the proposed study and establishes Independent Monitoring Committee (IMC). Membership in the IMC will be determined in collaboration with the NICHD program officer and the principal investigators and will include individuals that have expertise in chronic low back pain, biomechanics, clinical trials, and biostatistics.

The goals of the Data and Safety Monitoring Plan include 1) evaluation of the progress of the study, including periodic assessments of participant recruitment, accrual, retention, and timeliness; participant risk versus benefit; and other factors that can affect study outcome, and 2) consideration of factors external to the study, such as scientific developments that may have an impact on the safety of participants or the ethics of the study. A structured safety monitoring system will be established to both assure real-time participant care and unbiased monitoring of Adverse Events (AE).

The IMC will be scheduled to meet annually to conduct safety reviews. These meetings will cover all aspects of study progress, including participant recruitment, accrual, and retention; a review of data collection forms for assurance of data quality and timeliness; consideration of participant risk versus benefit; and other factors that can affect study outcome including a review of incidents of protocol deviation and actions taken in response to such deviations. In addition, these meetings will address any factors external to the study (e.g., recent scientific developments) that may have an impact on the safety of participants or the ethics of the study.

In addition to scheduled annual meetings, the IMC will also be consulted on an as-needed basis in the case of unanticipated serious adverse events or otherwise difficult situations that may arise. In such cases IMC members will discuss and implement the appropriate course of action to remedy any critical incident that may occur during the course of the study. A journal will also be maintained during the project to record the nature of any such critical incident, personnel involved, solutions considered, and the final action implemented to resolve the incident. Reporting of such critical incidents will be made to the Virginia Commonwealth University IRB as well as the NICHD. The IMC will also have responsibility to make recommendations to NICHD, the IRB, and the PIs concerning continuation or conclusion of the study, or possible modification of the ongoing protocol.

8. INTERVENTION DISCONTINUATION

A subject would be discontinued from the study intervention if a medical condition develops that precludes the continuation of the treatment intervention. For participants who discontinue The VIGOR Study prior to completing all scheduled treatment sessions (regardless of the reason), we will make every attempt to obtain

the outcome measurements. If the study participant is unwilling or unable to undergo the laboratory-based tests (e.g., difficulty tolerating the protocol, experienced an adverse event to a lab test) we will still attempt to obtain the clinical outcome measures. In instances where an adverse event does occur, we will follow-up with participants until the event is resolved or until the IRB deems it unnecessary to continue to follow the participant.

9. STATISTICAL CONSIDERATIONS

The co-primary clinical outcomes are changes in pain and disability. We will examine immediate clinical outcomes as a function of treatment. Relative to the control group, participants in the experimental group will show greater reductions in pain and disability at post-treatment relative to pre-treatment baseline (Hypothesis 1). To test Hypothesis 1, we will examine the Treatment by Time (baseline-post treatment) interaction in a LME model: a greater reduction in pain and disability in the experimental group than in the control group. The co-primary clinical outcomes of changes in pain and disability will be assessed at 1-, 6-, 12-, 24-, and 48-weeks post-treatment.

Secondary objectives are to examine potential mechanisms of pre- to post-treatment changes in clinical outcomes and maintenance of treatment gains. Participants in the experimental group will exhibit greater pre- to post-treatment decreases in pain/harm expectancy and increases in lumbar flexion as compared to the control group (Hypothesis 2.1). Decreases in pain/harm expectancy and increases in lumbar flexion will be positively related to pre- to post-treatment reductions in pain and disability (Hypothesis 2.2). Examination of maintenance of treatment gains will occur at 1-, 6-, 12-, 24-, and 48-weeks post-treatment. Relative to the control group, participants in the experimental group will continue to show lower levels of pain and disability at each time point as well as increased activity in their natural environment (Hypothesis 3).

This project is a Phase II RCT in which CLBP participants will be randomly assigned to one of two intervention arms. Those assigned to the experimental group will play immersive games that will encourage progressively larger lumbar flexion excursions at each game level and across treatment sessions. Those in the control group will play the same immersive games, but the parameters of the game will require smaller excursions of lumbar flexion to successfully complete gameplay. Treatment frequency and duration is based on existing evidence that graded activity and graded exposure interventions, typically lasting 6-12 weeks with 8-18 treatments sessions, result in significant reductions in disability.^{44,43} Accordingly, participants in this study will complete 18 visits over 9 weeks with the number of sessions tapered across weeks (i.e., 3 sessions/week in weeks 1-3, 2 sessions/week in weeks 4-6, and 1 session/week in weeks 7-9). Our co-primary outcome variables will be change in pain and change in disability from baseline to 1-week post-treatment (Aim 1). We will also examine changes in expectations of pain/harm and lumbar flexion as potential mechanisms of change in pain and disability (Aim 2). Aim 3 will examine maintenance of treatment gains at 1-, 6-, 12-, 24-, and 48-weeks post-treatment.

9.2 Sample Size and Randomization

We will recruit 230 participants with chronic low back pain (CLBP) and fear of movement. We will include participants with CLBP between the ages of 18-60 and who report no health condition(s) that may restrict movement or preclude safe participation. Participants will be recruited from the general population and specific

organizations such as Virginia Commonwealth University's University Medical Associates.

Aim 1: Power analyses were conducted to determine the sample size needed to achieve clinically important differences in our co-primary clinical outcome measures of pain and disability. Based on the extant literature, we based our analyses on a \geq 30% decrease in pain ratings¹ (on the 0-10 NRS scale) and a 30% decrease in disability ratings on the RMDQ² in the experimental group. Further, we predict a 10% decrease in pain and disability in the control group to account for potential placebo effects. The population standard deviations were set at 75% of the population mean values. The pre-post correlation was estimated as $r=0.7$. These population parameters translate into an effect size of $f=0.30$. Using these parameters, we drew 10,000 samples from a normal population distribution. Based on these parameters, to achieve power of 80% and $\alpha=0.05$ will require a total $N=78$.

Aim 2 & 3: Power analyses were conducted to determine the sample size needed to address hypotheses 2.1, 2.2, and 3. Using the method described by Morris (2008),³ we calculated effect size estimates from randomized clinical trials on the effects of graded activity or graded exposure interventions on changes in disability among individuals with CLBP.⁴⁻⁷ For our power analyses, we adopted the median estimated effect size: $\delta = .45$, which corresponds to what would commonly be described as a medium effect size. Following Raudenbush and Liu's (2000) recommendation,⁸ we set the residual error variance to 1 and estimated the between-subject slope variance to be 0.30. For power equal to .80 and $\alpha=0.05$, a sample size of 209 participants was indicated.

Based on the sample size calculations, using a sex-stratified random allocation table, we need a minimum sample of 209 participants to address Aims 1-3. To allow for 10% attrition from baseline to 48-week follow-up, we will recruit 230 participants.

Treatment Assignment Procedures

Randomization & Stratification: The study statistician will use the R statistical language to block randomize treatments stratified by sex. Then the study coordinator will assign subjects to the treatment arms.

Masking or Blinding: The principal investigators, the statistician, and members of the data collection team will remain blinded to intervention assignment throughout the duration of the study. They will be given the identifying codes only at the end of the study when it is necessary to interpret the results. The un-blinded study coordinator, who is responsible for scheduling testing and treatment sessions, will serve to receive the study patients and escort them to the various testing and treatments sites to minimize the interaction between patients; however, the study coordinator will not participate in the assessments.

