4.1 Inclusion Criteria

Participants must meet all of the following inclusion criteria:

- 18-60 years of age
- Low back pain that has been ongoing for at least half the days in the last 6 months
- Average pain intensity of 3 or higher over the past week on a 0-10 Numerical Rating Scale
- Disability >4 on Roland and Morris Disability Questionnaire
- Tampa Scale for Kinesiophobia score >36
- Has sought care or consultation from a health care provider for back pain
- Meets category < 4 on the Classification System of the Quebec Task Force on Spinal Disorders,⁴⁹ which reflects low back pain without neurological signs
- Working proficiency in English

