6.2 Description of Evaluations

Numeric Pain Rating Scales - Right now, 7-day & 24-hour: To assess pain, separate ratings of back pain intensity “right now”, over the preceding 24 hours, and over the preceding 7 days will be measured using an 11-point numerical rating scale (NRS) with anchors of 0 (No pain) and 10 (Pain as bad as you can imagine). This scale will quantify the study candidates rating of their low back pain symptoms.

Roland-Morris Disability Questionnaire: To assess physical functioning will be using the Roland-Morris Disability Questionnaire (RMDQ).^{50,51} The RMDQ includes 24 yes/no items that are designed to assess physical disability related to CLBP. This form quantifies the self-report level of disability.

Fear Question: Candidates will be screened for participation in the pre-screening and the full screening by indicating whether or not they agree with the statement “It is not really safe for a person with my back problem to be physically active.” An affirmative response will indicate a fear of movement.

Medical History – Back Pain: This form documents the candidate’s history of back pain.

Medication Log: To assess pain, participants will be asked to report current frequency and dosage of medications used for back pain. Additionally, all medication use will be documented in this form.

Informed Consent Form: Subjects must provide written informed consent prior to beginning the screening process and prior to implementation of any study procedures.

Inclusion/Exclusion Criteria: This form will document whether the study candidate meets all of the inclusion and exclusion criteria.

Enrollment/Randomization: This form will note the enrollment and randomization dates.

Medical History: To monitor safety, participants will complete a brief health screening at the beginning of each game session to determine if there are any changes in back pain or radiating symptoms.

Physical Exam Form: This form documents the study candidate’s physical exam

findings.

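### The Aim 1 planning SD of 75% of the mean cannot hold for 7-day pain at entry, where eligibility caps the ratio at 64%

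*Combined protocol and SAP*

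**What the plan says.** Section 9.2 and the Précis (Sample Size and Population) give the same Aim 1 inputs. The experimental arm is to improve by 30% on each co-primary outcome; for disability this is a "30% decrease in disability ratings on the RMDQ". For the control arm, "we predict a 10% decrease in pain and disability in the control group to account for potential placebo effects". On variability: "The population standard deviations were set at 75% of the population mean values". The pre-post correlation is 0.7. Samples were drawn from a normal distribution, and the result is given as f = 0.30 and a total N of 78 for 80% power at alpha 0.05. No mean in scale points and no source for the 75% appear.

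Section 4.1 restricts both outcomes at entry: "Average pain intensity of 3 or higher over the past week on a 0-10 Numerical Rating Scale" and "Disability >4 on Roland and Morris Disability Questionnaire". Section 6.2 fixes the upper ends. The pain scale has "anchors of 0 (No pain) and 10 (Pain as bad as you can imagine", and "The RMDQ includes 24 yes/no items that are designed to assess physical disability related to CLBP". Entry scores therefore lie in 3-10 for past-week pain and 5-24 for the RMDQ.

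Section 9.5.1 takes the co-primary baseline at Visit 1. Section 6.1 lets that fall on the screening day, and Section 6.1.1 allows up to 7 days after it. Section 6.2 defines three pain recall periods (right now, 24 hours, 7 days), and the plan does not say which is the co-primary one. Enrolment is set at 209 from Aims 2 and 3, said to cover Aims 1-3, and raised to 230 for 10% attrition.

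**The concern.** An entry threshold cuts off the low end of a scale. That raises the mean and narrows the spread, so the SD/mean ratio falls. A ratio of 75% is large for any score with a floor well above zero, and Section 9.2 does not mention the restriction. The SD is the input that converts a 20-point percentage difference in change into an effect size. If it does not describe the people being enrolled, the Aim 1 requirement and the statement that 209 suffices for Aim 1 have no stated basis. There is also a practical risk: someone who only recomputes N from the printed 75% gets a figure above 230 and may treat the co-primary comparison as underpowered because of an input that eligibility contradicts.

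**Working it through.** **Inputs.** Difference in change = 30% - 10% = 20% of the baseline mean; SD = 75% of the mean; r = 0.7; alpha 0.05; 80% power (all Section 9.2). Assumed, because not stated: two-sided test, 1:1 allocation, equal SDs at both times and in both arms, change-score comparison. N is from the noncentral t distribution.

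**1. The plan's own figure.** SD of change = 0.75 × sqrt(2(1 - 0.7)) = 0.581 of the mean. d = 0.20/0.581 = 0.344, f = d/2 = 0.17, N = 268. The printed f = 0.30 and N = 78 are not reproduced. f = 0.30 taken directly gives N = 90. An SD near 43% of the mean would give f = 0.30, and one near 40% gives N = 78. This mismatch is a separate defect; what follows concerns the 75% itself.

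**2. Ceiling on the ratio at entry.** For any variable on [a, b] with mean m, SD ≤ sqrt((m - a)(b - m)). The largest SD/mean is (b - a)/(2 sqrt(ab)), reached at m = 2ab/(a + b) with everyone at a or b.

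- 7-day pain, [3, 10]: 7/(2 sqrt(30)) = 0.639 at m = 4.62, with 77% of patients at 3 and 23% at 10.
- RMDQ, [5, 24]: 19/(2 sqrt(120)) = 0.867 at m = 8.28.

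| Mean pain | Largest possible SD | SD at 75% |
|---|---|---|
| 4 | 2.45 | 3.00 |
| 5 | 3.16 | 3.75 |
| 6 | 3.46 | 4.50 |
| 7 | 3.46 | 5.25 |

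So 75% is unattainable for entry pain at any mean. For the RMDQ it is attainable, but needs scores piled up near the two ends of the range. A flat spread over the integers gives 2.29/6.5 = 0.35 for pain and 5.77/14.5 = 0.40 for the RMDQ.

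**3. The simulated population.** A normal distribution with SD = 0.75 × mean puts 9.1% of scores below 0. For means of 4 to 7 it puts 37% to 22% of scores below the entry limit of 3.

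**4. Visit 1.** If a share p scores 0 and the rest have SD/mean = c, then 1 + 0.75² = (1 + c²)/(1 - p), so p = 1 - (1 + c²)/1.5625. With the rest split between 3 and 10 (c = 0.639), p = 9.9%. With c between 0.25 and 0.40 (assumed), p is 32% to 26%.

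**5. Effect on Aim 1**, other inputs kept; 207 analysed = 230 × 0.9:

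| SD/mean | f | N for 80% | Power, 207 analysed |
|---|---|---|---|
| 75% | 0.17 | 268 | 69% |
| 64% | 0.20 | 196 | 82% |
| 50% | 0.26 | 120 | 96% |
| 40% | 0.32 | 78 | over 99% |

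**6. Dropping equal SDs or r = 0.7** (assumed values, for illustration):

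- Entry SD 40%, follow-up SD 75% of the baseline mean, r = 0.7: SD of change = sqrt(0.16 + 0.5625 - 2 × 0.7 × 0.40 × 0.75) = 0.55, N = 240.
- SD 64% at both times: r = 0.64 gives N = 234, and r = 0.60 gives N = 260.

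**The case against.** Four points can be made on the other side.

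- **The bound covers less than the planning input does.** A reader might infer that 75% is impossible for the co-primary outcomes in general. The documents do not support that. Eligibility limits the past-week score at screening. The analysed baseline is at Visit 1, possibly on a different recall period, and a right-now or 24-hour score can be 0 in an eligible patient. The RMDQ ceiling is above 75%, and post-treatment pain has no floor at 3. All of this stands, and the point is limited accordingly.
- **An overlarge SD errs on the safe side.** Taken alone, it overstates N. A reader might go further and infer that any SD possible at entry needs fewer than 230. That holds only with equal SDs and r fixed at 0.7. Follow-up SDs may be wider, and a restricted entry range tends to lower the pre-post correlation; step 6 shows requirements of 234 to 260. The opposite inference, that 230 is too few because 75% gives 268, rests on the value that entry pain cannot have.
- **The 75% may be a misdescription.** An SD near 40% gives exactly N = 78, so the printed N may not have come from 75%. This is plausible but cannot be confirmed from the documents. It is a further reason to correct the figure.
- **Nothing in the conduct of the trial changes.** Enrolment rests on 209 from Aims 2 and 3. That is true, and it limits the consequence. However, Section 9.2 also says 209 suffices for Aim 1, and that statement depends on these inputs.

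**Conclusion.** Wrong as written, within a limited scope. The stated SD of 75% of the mean conflicts with the plan's own eligibility for 7-day pain at entry, where 64% is a mathematical ceiling that depends only on the 3-10 range. At Visit 1 it is implausible: at least about 10% of patients would have to score 0 even in the most extreme split. For the RMDQ it is possible but needs something close to a two-point distribution. For post-treatment pain the entry limit says nothing.

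The choice of SD moves the Aim 1 requirement from 268 (at 75%) to 196 (at the ceiling) or 78 (at 40%), given equal SDs, r = 0.7, a two-sided 0.05 test and a change-score analysis. Because follow-up SDs and r are also unsupported for this population, whether 230 is adequate for the co-primary comparison cannot be settled from the documents.

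**What to change.** In Section 9.2 and the Précis, replace the 75% with baseline and follow-up means and SDs in scale points. Give them separately for the NRS (naming the recall period) and the RMDQ, for people who meet the entry criteria, and with a source. The team's earlier chronic low back pain trials cited in Section 4 are one candidate, provided their entry limits are comparable. If no source exists, show a range over baseline SD, follow-up SD and r.

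Rerun the existing simulation with those inputs and restate f, the Aim 1 N and the power at 230 recruited. In the same edit, correct the separate mismatch that f = 0.30 and N = 78 do not follow from 75%.

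The cost is one rewritten paragraph in two places and a rerun of the simulation. Enrolment stays as planned. The downside is that the stated Aim 1 figures may change.

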We will recruit 230 participants with chronic low back pain (CLBP) and fear of movement. We will include participants with CLBP between the ages of 18-60 and who report no health condition(s) that may restrict movement or preclude safe participation. Participants will be recruited from the general population and specific organizations such as Virginia Commonwealth University's Medical Associates.

Aim 1: Power analyses were conducted to determine the sample size needed to achieve clinically important differences in our co-primary clinical outcome measures of pain and disability. Based on the extant literature, we based our analyses on a \geq 30% decrease in pain ratings¹ (on the 0-10 NRS scale) and a 30% decrease in disability ratings on the RMDQ² in the experimental group. Further, we predict a 10% decrease in pain and disability in the control group to account for potential placebo effects. The population standard deviations were set at 75% of the population mean values. The pre-post correlation was estimated as $r=0.7$. These population parameters translate into an effect size of $f=0.30$. Using these parameters, we drew 10,000 samples from a normal population distribution. Based on these parameters, to achieve power of 80% and $\alpha=0.05$ will require a total $N=78$.

Aim 2 & 3: Power analyses were conducted to determine the sample size needed to address hypotheses 2.1, 2.2, and 3. Using the method described by Morris (2008),³ we calculated effect size estimates from randomized clinical trials on the effects of graded activity or graded exposure interventions on changes in disability among individuals with CLBP.⁴⁻⁷ For our power analyses, we adopted the median estimated effect size: $\delta = .45$, which corresponds to what would commonly be described as a medium effect size. Following Raudenbush and Liu's (2000) recommendation,⁸ we set the residual error variance to 1 and estimated the between-subject slope variance to be 0.30. For power equal to .80 and $\alpha=0.05$, a sample size of 209 participants was indicated.

Based on the sample size calculations, using a sex-stratified random allocation table, we need a minimum sample of 209 participants to address Aims 1-3. To allow for 10% attrition from baseline to 48-week follow-up, we will recruit 230 participants.

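### The Aim 1 effect size of 0.30 and total of 78 do not follow from their stated inputs for the Hypothesis 1 test, which give f of 0.17 to 0.18 and 236 to 268 analysed for 80% power

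*Combined protocol and SAP*

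**What the plan says.** Section 9.2, repeated in the Précis under Sample Size and Population, gives these Aim 1 inputs: a fall of at least 30% in pain and "a 30% decrease in disability ratings on the RMDQ" in the experimental arm, a 10% fall in both outcomes in the control arm, and a pre-post correlation of 0.7. On spread it says "The population standard deviations were set at 75% of the population mean values". It then states "These population parameters translate into an effect size of $f=0.30" and, from 10,000 simulated normal samples, that 80% power at alpha 0.05 "will require a total $N=78".

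The Aims 2 and 3 calculation gives 209. The section concludes "we need a minimum sample of 209 participants to address Aims 1-3" and "To allow for 10% attrition from baseline to 48-week follow-up, we will recruit 230 participants".

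Section 9 defines the test for Hypothesis 1: "we will examine the Treatment by Time (baseline-post treatment) interaction in a LME model". The outcome is defined there as "change in pain and change in disability from baseline to 1-week post-treatment (Aim 1").

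**The concern.** Every input needed to recompute f and N is on the page, and the test is named. The result should therefore be reproducible, yet the stated inputs imply a much smaller effect on the change scale than f = 0.30.

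At stake is the stated power for the primary hypothesis. With 78 said to be enough and 209 planned, a reader will take Aim 1 to be heavily over-powered, and may read a null primary result as stronger evidence against the intervention than the design supports. Anyone sizing a later trial from this text would also start from a wrong figure.

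**Working it through.** **Inputs** (section 9.2; test from section 9). Scale the baseline mean to 1. Post-treatment means are 0.70 (experimental) and 0.90 (control), so the difference in mean change is 0.20. The correlation is r = 0.7. Two things are not stated and are assumed here: a two-sided test and 1:1 allocation. With two time points, the Treatment by Time interaction is a two-sample comparison of change.

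**Trying to reproduce 0.30 and 78.** The only route found uses a different effect and a different test:
- The SD of all four cell means (1, 1, 0.7, 0.9) is 0.1225. Dividing by 0.75 × √(1 − 0.7) = 0.411 gives 0.298. This pools the time, group and interaction effects.
- Putting f = 0.30, r = 0.7 and two measurements into the repeated-measures formula for the group main effect gives N = 77, or 78 with equal arms (81% power at 78).

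That this is how the figures arose is an inference. The group main effect, averaged over baseline and post-treatment, is not Hypothesis 1. Under the stated inputs its own f is 0.05/0.75 = 0.067, with about 10% power at 78.

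**Effect size for the Hypothesis 1 test.** SD of change = √(s₁² + s₂² − 2·r·s₁·s₂); d = 0.20/SD; f = d/2.
- *Constant SD of 0.75:* SD of change = 0.75 × √(2 × 0.3) = 0.581; d = 0.344; f = 0.172.
- *SD at 75% of each cell's own mean* (0.75 at baseline; 0.525 and 0.675 post-treatment): the variances of change are 0.2869 and 0.3094, so the pooled SD is √0.2981 = 0.546; d = 0.366; f = 0.183.

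**Power per outcome and N** (noncentral t):

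| | Constant SD | Scaled SD |
|---|---|---|
| Power at 78, two-sided | 32.3% | 35.9% |
| Power at 207 | 69.3% | 74.6% |
| Power at 209 | 69.7% | 75.0% |
| Power at 230 | 73.9% | 79.0% |
| Total N for 80% | 268 | 236 |
| Detectable difference at 78 (80% power) | 37.3 points | 35.1 points |
| Detectable difference at 209 | 22.6 points | 21.3 points |
| Detectable difference at 230 | 21.6 points | 20.3 points |

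The assumed difference is 20 points. A 10,000-sample simulation of the change test agrees: 33% and 36% at 78, 70% and 75% at 209.

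**More favourable readings of the same comparison:**
- One-sided 0.05, change test: 45-48% at 78 and 80-84% at 209; N = 186-212.
- Baseline-adjusted, two-sided: 37-52% at 78, 77-91% at 209 and 80-94% at 230; N = 150-228.
- Baseline-adjusted, scaled SD, one-sided: 65% at 78; N = 118.

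**What f = 0.30 would require.** With constant SD, the change test reaches f = 0.30 only if r is about 0.90, the SD is about 43% of the mean, or the difference is about 35 points. None of these is stated. Even taking f = 0.30 as given for two groups (d = 0.60), N would be 90 two-sided or 72 one-sided.

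**Number available for Aim 1.** The 10% loss runs to week 48 (230 × 0.9 = 207), while the endpoint is 1 week after treatment. The relevant number therefore lies between about 207 and 230, and the shortfall from 80% on the two-sided written test is about 1 point (80 − 79.0) to 11 points (80 − 69.3).

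**The case against.** The strongest reply is that little depends on 78. Enrolment comes from the Aims 2 and 3 calculation, no one will analyse 78 participants, and a null result is properly read from its confidence interval rather than from planned power. That stands, and it limits the severity. It does not make the stated power correct.

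Second, the inputs may be pessimistic for pain. Entry requires pain of at least 3 on a 0-10 scale, and a variable confined to 3-10 cannot have an SD above 64% of its mean ((10 − 3)/(2√30) = 0.639). At that bound, with constant SD, power at 209 is about 83%. Pain is also given as a fall of at least 30%; a 23-point difference would give 81% at 209. Both points are fair for pain, although eligibility is rated at screening and post-treatment scores are not truncated. Neither covers disability, where the fall is fixed at 30% and the entry limit (above 4 on a 24-item scale) allows an SD up to about 87% of the mean. One N is given for both outcomes.

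Third, a one-sided or baseline-adjusted test could reach 80% at 209. That is true for some combinations, but the plan states neither, and none gives more than 65% at 78.

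Fourth, the figures may have a traceable origin. If so, it is a pooled effect size used with a group main-effect formula, which is not the Hypothesis 1 test.

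**Conclusion.** The concern holds. For the Hypothesis 1 test as written, f = 0.30 and N = 78 are wrong. The stated inputs give f of 0.17 to 0.18, 32-36% power at 78, and 236-268 analysed for 80%. At the numbers expected at the 1-week endpoint, power is about 69-79% per co-primary outcome, so the claim that 209 suffices for Aim 1 at 80% is not supported if the test is two-sided. Power to succeed on both outcomes would be lower.

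These figures rest on two-sided 0.05, 1:1 allocation and the unadjusted interaction; the ranges run from constant SD to SD scaling with each mean. The finding that 78 is too few does not depend on those choices: every reading of the Hypothesis 1 comparison that was tried falls short of 80% at 78. The error does not bias the estimate, inflate type I error or set enrolment. It should be fixed as a misstatement of power for the primary hypothesis.

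**What to change.** 1. In the Précis and section 9.2, replace f = 0.30 and N = 78 with figures that can be reproduced. For the written test, two-sided with 1:1 allocation, these are f of about 0.17 to 0.18 and 236-268 analysed for 80%.
2. State whether the SD is constant or scales with the mean, the sidedness, the allocation ratio, and the test that was simulated.
3. State Hypothesis 1 power at the number expected 1 week after treatment (between about 207 and 230).
4. In the same edit, reword the sentence that 209 is sufficient for Aims 1-3, so that the section does not contradict its corrected figures.
5. Optional: fit the Hypothesis 1 mixed model with a common baseline mean across arms, equivalent to adjusting for baseline. The current test is valid without this. At 209, two-sided, it would raise power from about 70% to 77% with constant SD, or from 75% to 91% with scaled SD. If adopted, restate power for that model.

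The cost is wording in two places, plus one line of model specification if the optional step is taken, using data already collected. The stated Aim 1 power becomes less favourable. No extra enrolment is requested.
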